6.16. Revision/Explant Procedure

Data to be collected prior to revision/explant:

- Medications
- Measurement and recording of electrode impedance as defined in the Implant and Programming Manual (system to be revised/explanted)

Data to be collected during or post revision/explant procedure:

- Surgical notes
- Adverse Events
- Measurement and recording of electrode impedance and stimulation thresholds as defined in the Implant and Programming Manual (newly implanted system)

NOTE: If the procedure occurs prior to 120 days, then the Subject should preferably be unconscious (i.e.: general anesthesia) during assessment of electrode impedance and stimulation thresholds. If local anesthesia is used, then appropriate medication should be administered to minimize the chance that the Subject will remember the procedure.

Activities to be performed after revision procedure:

- Make a (de-identified) digital record of fluoroscopic images taken during the implant procedure^h including at least bi-plane (AP and lateral) radiographic images of electrode position that shows the entire newly implanted system from the distal tip of the electrodes to the whole IPG
- Inspect the surgical site prior to hospital discharge
- Program IPG to OFF (i.e.: default state is no electrical output from the IPG)
- Continue with study required visits.

Activities to be performed after explant procedure:

- Explant <120 days post randomization
 - Subject will be followed until the 120 day visit and then exited.
- Explant >120 days post randomization
 - Adverse events will be collected over the last 30 days prior to exiting the study

^h It is a requirement for a site to participate in the trial that digital recording of fluoroscopic images should be available

7. Anticipated Benefits and Risks

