
Supporting Safety Analysis
	
The PMA Submission will include 12 month safety data on all Subjects implanted with ReActiv8 including all Subjects implanted in the ReActiv8-B Trial for whom 12 month safety data are available, and other persons implanted with ReActiv8 in other clinical trials (including the ReActiv8-A PMCF Study) and all post-marketing registries that are registered on www.clinicaltrials.gov.
 
A separate safety assessment will be performed on the Surgical Roll In group, including a poolability analysis.

Health Economics	
Cost-effectiveness of ReActiv8 therapy, extrapolated to the lifetime of the device, will be assessed. Key economic outcome measures to be recorded will include:
 
 • Change in work status at all visits. • Change in consumption of medications taken for low back pain at all visits compared to Baseline. • Assessment of health care utilization (office visits, hospital visits, emergency room visits, and other therapies such as physical therapy) at all visits. 
Note that the Health Economics assessment is likely to be incomplete at the time of PMA submission for ReActiv8, since not all Subjects will have reached the 12 month point at that time.

Efficacy Follow Up	All Subjects will be followed for efficacy until PMA approval unless the study is closed prior to PMA approval for any reason.
Safety Follow Up	All Subjects will be followed for safety until PMA approval or 7 years from the Baseline Visit, whichever is longer, unless the study is closed prior to PMA approval for any reason.
Device Data	At each follow up visit during which the ReActiv8 IPG will be interrogated, electrical parameters stored in the IPG such as lead impedance will be recorded. Results of threshold testing (if performed) and any reprogramming will be recorded.
Study Duration	
Anticipated to be ≤60 months from first Subject Baseline Visit to PMA submission.
 
Informed consent for all Subjects will allow for continuing collection of safety and efficacy data for a total period of 7 years from the Baseline Visit.

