4.7.4. Supporting Safety Analysis

The PMA Submission will include 12 month safety data on all Subjects implanted with ReActiv8 including all Subjects implanted in the ReActiv8-B Trial for whom 12 month safety data are available, and other persons implanted with ReActiv8 in other clinical trials (including the ReActiv8-A PMCF Study) and all post-marketing registries that are registered on www.clinicaltrials.gov. This data will be provided as a separate analysis of the safety on all implanted persons as an appendix to the ReActiv8-B Trial results.

A separate safety assessment will be performed on the Surgical Roll In Cohort, including a poolability analysis.

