7.2. Missing Data and Sensitivity Analyses

The primary efficacy endpoint will be assessed in the ITT Cohort, consisting of all randomized Subjects not in the Surgical Roll In Cohort, with missing endpoint assessments examined in sensitivity analyses. Secondary efficacy endpoints will be assessed in the population of Subjects with complete data (baseline and at the Primary Endpoint Assessment Visit). Sensitivity analyses of the impact of missing data will include a tipping point analysis for the primary efficacy endpoint where the endpoint is computed with possible combinations of imputed success and failure for Subjects with missing primary efficacy assessment. Additionally, for the primary and secondary efficacy endpoints, a last observation carried forward analysis will be conducted.

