8.8.2. Supporting Safety Analysis

The PMA Submission will include 12 month safety data on all Subjects implanted with ReActiv8 including all Subjects implanted in the ReActiv8-B Trial for whom 12 month safety data are available, and other persons implanted with ReActiv8 in other clinical trials (including the ReActiv8-A PMCF study) and all post-marketing registries that are registered on www.clinicaltrials.gov. This data will be provided as a separate analysis of the safety on all implanted persons as an appendix to the ReActiv8-B trial results.

A separate safety assessment will be performed on the Surgical Roll In Cohort, including a poolability analysis.

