8.9. Supporting Analyses

The supporting efficacy analyses will include:

- Once data are complete, all primary and secondary outcome measures will be assessed at 12 months and compared to baseline within the Treatment group. The analysis will also explore correlation of outcomes to amount of stimulation delivered.

a Cui, L., Hung, H. M., & Wang, S. J. (1999). Modification of sample size in group sequential clinical trials. *Biometrics*, 55, 853–857. doi:10.1111/j.0006-341X.1999.00853.x

Note: For all supporting analyses, amount of stimulation delivered will be defined as the number of minutes stimulation was delivered divided by the number of minutes that stimulation could have been delivered.

- In the Crossover Group, outcome measures will be assessed at the Outcome Post Crossover Visit for all Subjects who met the inclusion criteria for low back pain at the Primary Endpoint Assessment Visit (i.e.: prior to Crossover) (Prior week average Low Back Pain, VAS of ≥ 6.0 cm and ≤ 9.0 cm (on a 10cm scale)) and inclusion criterion for ODI (Oswestry Disability Index score $\geq 21\%$ and $\leq 60\%$). The analysis will also explore correlation of outcomes to amount of stimulation delivered.
- Comparison of daily average VAS averaged over the prior 7 days of Journal entry with the single point VAS of recollection of prior 7 days of average pain.
- Comparison of EQ-5D VAS between Treatment and Control groups at each visit at which EQ-5D is recorded through 12 months.
- For the both the Treatment and Control groups, a cumulative proportion of responder analysis, so that the entire distribution of treatment response is depicted in a graph of the proportion of responders for all percentages of low back pain VAS reduction from 0% to 100%. In this manner, the number of Subjects with $\geq 50\%$ low back pain VAS improvement can be determined, for example. The analysis will also be performed for the responder analysis of ODI.
- Subject Global Impression of Change at 12 months: The analysis will explore correlation of outcomes to amount of stimulation delivered.
- Treatment satisfaction questionnaire at 12 months: The analysis will explore correlation of outcomes to amount of stimulation delivered.
- Clinical Global Impression – Global Improvement (clinician assessment) at 12 months: The analysis will also explore correlation of outcomes to amount of stimulation delivered.

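### Protocol 6.16 exits explanted Subjects although other sections keep all Subjects in follow-up, and the 12-month analyses do not say how those who exit are counted

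*Protocol*

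**What the plan says.** **Exit after explant.** Protocol 6.16 treats explants by timing. Before day 120: "Subject will be followed until the 120 day visit and then exited". After day 120 the only instruction is: "Adverse events will be collected over the last 30 days prior to exiting the study". The date of that exit is not tied to the date of explant. Revision is treated differently; those Subjects are told to "Continue with study required visits".

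**Follow-up of everyone.** Table 1 (Protocol 2.4) states: "All Subjects will be followed for safety until PMA approval or 7 years from the Baseline Visit, whichever is longer", unless the study closes earlier. It also has all Subjects followed for efficacy until PMA approval. Protocol 6.13 schedules annual visits for all Subjects until US approval, and only after approval limits them to Subjects who still have the device.

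**12-month safety.** Protocol 4.7.4 and SAP 8.8.2 promise 12-month safety data on all implanted persons, "including all Subjects implanted in the ReActiv8-B Trial for whom 12 month safety data are available". Neither gives a denominator or an exposure rule.

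**12-month efficacy.** SAP 8.9 says that "all primary and secondary outcome measures will be assessed at 12 months and compared to baseline within the Treatment group". It names no analysis population and no handling of Subjects who have left.

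**Missing data.** SAP 7.2 has a complete-data rule, a tipping-point analysis and last observation carried forward. The complete-data rule names the Primary Endpoint Assessment Visit, and the other two apply to the primary and secondary endpoints, which SAP 8.1 places at that visit.

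**The concern.** ReActiv8 is meant as a permanent implant, and its 12-month safety data go into the PMA submission. Exit after explant is unlikely to be unrelated to outcome. The examples of explant in Protocol 6.14 are infection and removal at the Subject's request. Under Protocol 8, note 10, lack of efficacy is not an adverse event. A Subject explanted at month 6 for want of benefit would therefore generate no adverse event for that reason, would have no 12-month score, and might be visible only in the withdrawal summary of SAP 8.3.

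If the 12-month results are computed on those still present, they describe a group partly selected for tolerating and wanting the device. The event rate could then look too low and the responder rate too high. Separately, sites cannot follow 6.16 and Table 1 at the same time for an explanted Subject.

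**Working it through.** **1. Passages side by side.** Take a Subject explanted at month 5, before approval.

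- Protocol 6.16: exits, with adverse events collected over the final 30 days.
- Table 1: followed for safety to approval or 7 years from baseline, whichever is longer, and for efficacy to approval.
- Protocol 6.13: annual visits until approval, with no exception for explant.
- SAP 8.8.2: counted if 12-month safety data are available, without saying whether a record that ends at exit qualifies.
- SAP 8.9: no rule.

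The first three cannot all be followed. The last two leave the denominator open.

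**2. Inputs.** The documents give no 12-month rate and no explant rate, so there is no plan figure to reproduce on this point. The planned size does reproduce: 50% against 25%, two-sided 5%, 80% power gives 58 per arm, 116 in total, and 116 × 1.10 = 127.6, rounded to 128. With 1:1 allocation that is 64 Treatment Subjects. Protocol 4.4 gives up to 208 implanted and randomized including Surgical Roll In. All explant, response and event rates below are assumptions.

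**3. Efficacy.** Let *e* be the share explanted, *R* the responder rate in those retained, and *g* the responder rate in those explanted. The rate in all Treatment Subjects is *R*(1 − *e*) + *g e*, so leaving explants out shifts the result by *e*(*R* − *g*). With *g* = 0 and *R* near 50%:

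| Explants of 64 | Responders | Retained only | All 64 | Difference (points) |
|---|---|---|---|---|
| 1 | 32 | 32/63 = 50.8% | 50.0% | 0.8 |
| 3 | 30 | 30/61 = 49.2% | 46.9% | 2.3 |
| 6 | 29 | 29/58 = 50.0% | 45.3% | 4.7 |
| 10 | 27 | 27/54 = 50.0% | 42.2% | 7.8 |

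With *R* near 60% the differences run from about 1 to 9 points. If half of the explanted Subjects had responded (*g* = *R* = 50%), the difference would be zero; above that it changes sign.

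**4. Safety, only if data count as available solely for Subjects who reached the 12-month visit.** Assume about 2% of retained Subjects have a serious related event (4 events), with 208 implanted:

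| Explants | Retained only | All, half of explants due to such an event | All, every explant due to one |
|---|---|---|---|
| 4 | 4/204 = 2.0% | 6/208 = 2.9% | 8/208 = 3.8% |
| 10 | 4/198 = 2.0% | 9/208 = 4.3% | 14/208 = 6.7% |
| 21 | 4/187 = 2.1% | 14/208 = 6.7% | 25/208 = 12.0% |
| 31 | 4/177 = 2.3% | 20/208 = 9.6% | 35/208 = 16.8% |

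The last column is a worst case. With 128 implanted the pattern is similar: 1.6% against 3.9% with 3 explants, and 1.8% against 16.4% with 19. Under the other reading of availability the distortion does not arise.

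**The case against.** The strongest reply on safety is that nothing says events are removed. Adverse events are collected from consent and adjudicated (Protocol 8), removal for malfunction is itself a device-related event (note 11), and Protocol 2.4 defines a Safety Cohort of all enrolled Subjects with an attempted or successful implant. Protocol 4.7.4 and SAP 8.8.2 speak of all implanted persons. The qualifier on availability may refer only to Subjects who have not reached 12 months at submission, a situation the documents mention several times. This stands: the events are recorded. What is missing is a rule that they enter the 12-month rate. The Safety Cohort is not among the populations in SAP 8.2, and SAP 8.8.2 does not use it.

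On efficacy, a reader might infer that the 12-month results are restricted to Subjects with 12-month scores. The SAP does not say that. It is silent, and available-case analysis is only the likely default. Protocol 8, note 5, allows for removal because pain was relieved, so the direction of bias is not certain.

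A reader might also infer that device failures in general vanish, or that explanted Subjects leave soon after surgery. Revised Subjects stay in follow-up, and 6.16 does not link the exit date to the explant date.

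Finally, the 12-month efficacy analysis is supporting, within one arm, and without a hypothesis. That limits the consequence but does not remove it, since a fixed denominator costs little.

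**Conclusion.** The point holds as a contradiction on follow-up and an open denominator at 12 months. Protocol 6.16 conflicts with Table 1 and 6.13 whatever the size of any bias. The 12-month serious related event rate can be understated, under one permissible reading of SAP 8.8.2. The 12-month responder rate can be overstated, by about 1 to 8 points at assumed explant rates of about 2% to 15%, if half of retained Subjects respond and no explanted Subject benefited.

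The documents do not support the stronger conclusion that complications are lost or that the 12-month figures are certainly biased. The 120-day primary endpoint and the primary safety assessment are not affected by the exit rule, because Subjects explanted earlier are followed to that visit.

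**What to change.** - **Protocol Table 1, 6.13 and 6.16:** reconcile what follow-up applies after explant, until when, and how the exit date is set.
- **Protocol 4.7.4 and SAP 8.8.2:** report 12-month safety for all implanted ReActiv8-B Subjects, following the Safety Cohort idea of Protocol 2.4. Count every adjudicated event up to exit. Give cumulative incidence to 12 months, with Subjects in the risk set until exit or data cut-off, and list explants by reason. State that availability refers only to Subjects not yet at 12 months at the cut-off, if that is the intent.
- **SAP 8.9:** give the 12-month responder and resolution summaries with all Treatment Subjects due for 12 months as denominator. Count explant as non-response unless the recorded reason is pain relieved. Put the observed-case figure beside it.

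The cost is SAP and Protocol wording and one more table from data already collected. The 12-month figures may look somewhat less favourable. Remote collection of VAS after explant is not needed for this fix.

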7.1. Anticipated Benefits

The purpose of electrical stimulation of the medial branch of the dorsal ramus nerve with the ReActiv8 is to help restore neural drive to the lumbar multifidus muscle (LM). There are known clinical benefits to the restoration of neural drive to and rehabilitation of the LM when delivered by guided physical therapy with image guided biofeedback including:

- Improvements in the disabling effect of low back pain
- Improvements in severity of low back pain
- Reduction in recurrence of low back pain
- Improvement in ability to handle regular daily activities, including return to work
- Improvements in Quality of Life

Based on the Feasibility Study performed with other devices, there are expected benefits from the stimulation to be delivered by the ReActiv8, including decrease in low back pain, decrease in disability, and improvements in quality of life.

There may be no benefits to the Subject as a result of participation in this Trial.

7.2. Anticipated Risks

All medical device treatments have the potential to cause adverse events or side effects. Adverse events are expected to be similar to other neurostimulation devices for treatment of back pain, such as spinal cord stimulators. Listed in this section are both known risks with spinal cord stimulators and peripheral nerve stimulators as well as theoretical risks for the ReActiv8.

Additional information on risks and anticipated adverse events is to be found in the Implant and Programming Manual, which also includes warnings and precautions.

Anticipated Adverse Events include:

- AEs associated with the surgical procedure, including implant, revision, replacement and removal.
 - Acute or persistent pain including more pain than anticipated after surgery or worsened low back pain
 - Accidental injury to adjacent tissues, e.g. piercing structures such as muscle, blood vessels, nervous tissue, or organs
 - Anxiety about surgical procedure or outcome of therapy (beyond what is reasonably expected)
 - Infection, including local infection of the device or surgical site, systemic infection and sepsis
 - Respiratory arrest, e.g. apneic spell during surgery
 - Slow, abnormal or inadequate wound healing including swelling, hematoma, seroma, or wound dehiscence, which may require surgical repair
 - Nerve irritation, impingement or damage, including pain, paralysis, sensory deficits or changes to bowel, bladder or reproductive function
 - Scarring or inflammation associated with the surgical site (beyond what is reasonably expected)
 - Stiffness or restriction in movement
 - Death

- Risks associated with any surgical procedure, regardless of type, including prolonged procedure or sequelae of anesthesia
- Bleeding, hematoma, and bruising
- Swelling (beyond what is reasonably expected), seroma, or cyst
- Abandonment of implant procedure, including due to failure to achieve suitable stimulation thresholds in one or both leads
- Intraoperative difficulties implanting the device, such as inadequately seating lead into connector or damage to lead insulation
- Tissue reaction to the presence of the implanted device or materials in/on the implanted device such as response to residual material on device or an allergic response, e.g. previously unknown nickel or titanium allergy. Reaction may be local or systemic.
- AEs associated with presence and use of the device. This includes AEs associated with chronic implant whether or not the device is turned on.
 - Migration of the lead, which may result in surgical revision, replacement or removal of device
 - Device failure including failure of the IPG, failure of the lead, or failure of any other implanted component which may necessitate surgical revision, replacement, or removal of the device or components of the device.
 - Nerve irritation, impingement or damage, including that resulting from mechanical presence of device, exposure to electricity including electrical stimulation, or migration of the leads, suture sleeve or IPG. This may lead to pain, paralysis, sensory deficits or changes to bowel, bladder or reproductive function
 - Device extrusion
 - Erosion, threatened erosion or fistula formation in skin overlying device components
 - Excessive fibrotic tissue growth, including fibrotic tissue growth which may complicate device removal.
 - Hematoma, seroma, cyst or swelling
 - Acute or persistent pain including worsened low back pain and/or pain and discomfort due to presence of the device
 - Undesired sensations such as uncomfortable paresthesia, numbness, vibration, pressure, prickling, or uncomfortable contraction of the multifidus
 - Overstimulation of tissue, resulting in symptoms such as painful muscle contraction, paresthesia, jolts or shocks. In addition, injuries that occur as a consequence of stimulation, e.g. accidents that occur as a result of being startled or back injuries that occur due to diminished motor control
 - Infection, including local infection of the device or surgical site, systemic infection and sepsis
 - Death
 - Tissue reaction to the presence of the implanted device or materials in/on the implanted device such as response to residual material on device or an allergic response, e.g. previously unknown nickel or titanium allergy. Reaction may be local or systemic.
 - Skin irritation as a result of contact with the Activator
 - Tissue damage due to mechanical presence of device, or exposure to electricity including electrical stimulation
 - Contraction of muscles other than the target muscle(s)
 - Muscle fatigue, spasm or injury
 - Malfunction of other medical equipment such as a pacemaker due to device interactions
 - Stiffness, including restricted motion due to adhesions to the device
 - Psychiatric disturbance, such as anxiety or depression or complications of depression such as suicide

- Symptoms in unrelated systems such as nausea, insomnia, urinary retention or undesired weight changes, including as a sequelae of stimulation of the Subject.
- Inability to deliver therapy, including inadequate doses of therapy. Sources include lead migration, device malfunction or exposure to electromagnetic fields, e.g. security screening devices
- Electrical shock
- Inability to stop therapy, with possible sequelae such as anxiety, restriction of movement, pain, muscle fatigue, postural changes, difficulty in walking, sitting or physical activity
- Accidents, injuries, body movements, body positions or biological process which lead to device complications such as a fall which causes injury to the IPG, sit-ups or severe coughing leading to migration of the lead, or bony fracture leading to device migration or fracture.

Subjects may also undergo medical/and or surgical intervention to treat the issues identified above.

The ReActiv8 includes features that provide protection from EMI. Most electrical devices and magnets encountered in a normal day are unlikely to affect the operation of the ReActiv8. Sources of strong EMI can exist near high power amateur radio transmitters, near television towers or other equipment. Generally, the amount of EMI present in publicly-accessible areas is reduced to a level that is not likely to impact the ReActiv8. Exposure to strong sources of EMI can result in the following effects:

- Serious injury or death, resulting from heating of the implanted components of the ReActiv8 and damage to surrounding tissue.
- Damage to the ReActiv8, resulting in a loss of or change in stimulation delivery and requiring surgical replacement.
- Operational changes to the ReActiv8 IPG, causing it to turn ON or OFF (particularly if the IPG is enabled for magnet use) or to reset, resulting in loss of stimulation and requiring reprogramming by a clinician.

Equipment such as retail theft prevention systems and airport metal detectors may interfere with the ReActiv8. The Subject should be instructed to walk directly through such systems and not remain near them any longer than necessary. The presence of an implantable pulse generator in the body may set off security screening devices (e.g.: at airports), so it will be necessary for the Subject to carry a card to identify themselves to security screeners as carrying an IPG.

Subjects with either the study device implanted or parts of the study device still implanted will not be able to have a magnetic resonance imaging (MRI) scan, since this test may damage the study device and may cause serious injury. This risk is unchanged as long as the system (IPG and leads) remains implanted.

